8.1.2 Data Handling for Subjects Who Withdraw/Drop Out from the Study

Subjects who withdraw/drop out from the study will have the early termination (ET) data collected at their ET visit included in the analysis at the closest visit (Week 2, 6, 10, 14), using midpoints between visits to window the early termination. If this results in two records for a given visit, then the one closest to the targeted date will be used.

For example, a subject with valid Week 10 clinic assessment collected on Day 72 that has early termination data collected on Day 79, would have the early termination data mapped to Week 10; however, since Day 72 data is present and closer to the target date, it would be analyzed and the Day 79 data would be excluded. A subject without valid Week 10 data who early terminates on Day 79 would have the Day 79 data analyzed with the Week 10 data.

Subjects who provide 14 weeks of diary pain data will be analyzed as completers for purposes of the primary analysis, even if for some reason they are unable to attend a Week 14 final study visit. As a specific example, a subject who successfully provides 14 weeks of diary data as described in [Section 8.2.1](#), but who is unable to attend a final study visit during the required time window because of travel or other circumstances, would be analyzed as a completer for purposes of the primary endpoint, but would be missing non-diary based secondary outcome measures at

the Week 14 endpoint. For safety data, the last observation available will be summarized in addition to the presentation above (grouping ET visits with the closest planned visit); this will combine the ET visit data with the completers' Week 14 data, regardless of when the ET occurred.

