11.3. Visit 3 (Week 2)

Visit 3 should occur after 2 weeks of treatment, on Day 15 -4/+7 days. For those patients unable to return to the site (i.e. extenuating circumstances due to COVID-19 pandemic), a telephone visit is an option. All assessments should be performed with exceptions of the ones specifically noted with comments in parenthesis.

The following assessments and procedures are scheduled for this visit in the following general order:

- Review completed diary data and diary compliance with the patient
- Assess changes in medication history and concomitant medications

- Assess study drug compliance and collect previously dispensed study drug and bottle (Telephone visit exception - patient will be instructed to count the number of tablets remaining in their current bottle(s), document this on a patient provided form, and return this form with the study drug (including bottle(s)) to the site for assessment of compliance in a pre-paid pre-addressed courier envelope supplied in a “tele-visit” package to patient).
- Have the patient complete the BDI-II
- Administer the “Since Last Visit” version of the C-SSRS
 - a. Results of the C-SSRS and BDI-II should be reviewed together to ensure (1) the patient is not experiencing suicidal ideation or worsening depression that requires intervention and (2) both scales are providing a consistent clinical picture of the patient with regard to suicidality. (Telephone visit exception – response to Question #9 of the BDI-II is reviewed with the patient and C-SSRS is administered over the phone).
- Assess occurrence of adverse events
- Have the patient complete all PROs (Telephone visit exception – all PROs should be mailed ahead of the visit and returned to the clinic after completion via courier):
 - a. PGIC
 - b. FIQR
 - c. Clinic administered assessment of pain by both 24-hour and weekly recall using 11-point (0-10) NRS scale
 - d. PROMIS scales for sleep disturbance and fatigue
- Ensure that all PROs were accurately and fully completed
- Vital signs (Telephone visit exception – vital signs are not required)

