8.2.6 Changes in Sexual Functioning Questionnaire Short-Form (CSFQ-14)

The CSFQ-14 ([Keller et al. 2006](#)) is validated scale with internal reliability designed to allow a patient to self-evaluate his or her sexual behaviors or problems in a number of areas. The CSFQ-14 will be administered at Baseline (Visit 2) and Week 14/ET (Visit 6). It yields a total score, three subscales corresponding to phases of the sexual response cycle (i.e. desire, arousal, orgasm), and five subscales corresponding to important dimensions of sexual functioning. It is considered a useful scale for assessing sexual side effects of medications. For all items, higher scores reflect higher sexual functioning. For 12 of the 14 items, higher sexual functioning corresponds to greater frequency or enjoyment/pleasure (e.g. 1=never to 5 = every day). For two items (item 10, assessing loss of interest after arousal for women and priapism for men, and item 14, assessing painful orgasm), higher sexual functioning corresponds to lower frequency (e.g. 1=every day; 5=never). Items 10 and 14 are included in the total score but not in any subscale scores.

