10.3 Exploratory Analyses

All efficacy analyses at time points other than Week 14 are considered exploratory as described above.

Additional exploratory efficacy endpoints include:

- FIQR total score, overall impact domain score, and individual item scores at all post-randomization clinic visits
- Proportion of subjects with a $\geq 30\%$ improvement from baseline to Weeks 1-14 in the daily self-reported pain severity score
- Proportion of subjects with a $\geq 50\%$ improvement from baseline to Weeks 1-14 in the daily self-reported average pain severity scores
- PGIC as a continuous variable with 1-7 scoring
- CSFQ-14 at Week 14
- In-clinic assessment of pain (24-hour & weekly recall)
- Permutation test of change from baseline in the weekly average of the daily pain scores at week 14.

The proportion of improvement endpoints will be analyzed in using a logistic regression model for each week with effects for treatment and investigative site. If the model does not converge, site will be removed from the model. Subjects with missing data will be considered non-responders. In addition, odds ratios and corresponding 95% CI intervals for being a pain responder will be presented.

In addition to the responder analysis in the secondary outcomes, PGIC will be analyzed as a continuous variable scoring the responses 1-7. Results will be reported by treatment with summary statistics and an MMRM Model will be used to compare treatments. The model will include the fixed, categorical effects of treatment, site, study week, and treatment by study week interaction. An unstructured covariance structure will be used to model the within-subject errors. If this analysis fails to converge, the following structures will be tested in this order: first order ante dependence, heterogeneous first order autoregressive, heterogeneous compound symmetry and compound symmetry with the first to give convergence used. The Kenward-Roger approximation will be used to estimate the denominator degrees of freedom. Significance testing will be based on least-squares means using a two-sided $\alpha=0.05$ test and two-sided 95% confidence intervals will be presented.

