The CSFQ-14 is completed at baseline and Week 14/ET. It has a male and a female version, which will be analyzed separately. The CSFQ-14 will be analyzed for its total score, three subscales on phases of sexual response, and five subscales for dimensions of sexual functioning by using an Analysis of Covariance (ANCOVA) model. The model will include the fixed, categorical effects of treatment and site, plus a baseline covariate corresponding to the subscale (or total) being analyzed. Significance testing will be based on least-squares means using a two-sided $\alpha=0.05$ test and two-sided 95% confidence intervals will be presented. This outcome is considered to be supportive of the product's safety; other exploratory analyses are for further support of product efficacy.

The FIQR exploratory endpoints and the in-clinic pain assessments will be analyzed using an MMRM including the fixed, categorical effects of treatment, site, study week, and treatment by study week interaction, as well as the fixed covariates of baseline value and baseline value score-

by-study week interaction. An unstructured covariance structure will be used to model the within-subject errors. If this analysis fails to converge, the following structures will be tested in this order: first order ante dependence, heterogeneous first order autoregressive, heterogeneous compound symmetry and compound symmetry with the first to give convergence used. The Kenward-Roger approximation will be used to estimate the denominator degrees of freedom. Note that the screening values will be used as baseline for the in-clinic pain outcomes.

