11.2 Clinical Laboratory Evaluations

Laboratory data (analytes for Chemistry and Hematology) will be summarized by treatment and visit for the Safety Population. Descriptive summaries of actual values and changes from baseline will be presented by study visit and last available assessment for each clinical laboratory analyte and each treatment group. 95% confidence intervals will be presented for change from baseline. ET data will be analyzed with the closest visit that does not have a valid assessment value.

Laboratory values will be displayed in the data listings with their corresponding normal ranges, and those values that are outside the normal range will be flagged. For each laboratory analyte, shifts in assessments of abnormality from baseline to each scheduled time point will be presented in shift tables.

A by-subject listing of all clinical laboratory (Chemistry, Hematology and Urinalysis) data will

also be provided.

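### Read literally, the SAP's early-termination windowing rule keeps most early terminators' CSFQ-14 scores out of the only CSFQ-14 analysis

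*SAP*

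**What the plan says.** **Collection.** Protocol Table 2 schedules the CSFQ-14 at Visit 2 and at Week 14/ET and nowhere else. Protocol 11.5.2 includes it among the questionnaires completed at an ET visit. SAP 10.3 agrees: "The CSFQ-14 is completed at baseline and Week 14/ET".

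**Windowing.** SAP 8.1.2 states that ET data are "included in the analysis at the closest visit (Week 2, 6, 10, 14), using midpoints between visits to window the early termination". Where a visit then has two records, the one nearer the target day is kept. No instrument is exempted. For safety data the section adds a last-observation summary that pools ET values with completers' Week 14 values.

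**Analysis.** SAP 10.3 lists the endpoint as "CSFQ-14 at Week 14". It specifies an ANCOVA, separately for the male and female versions, with treatment, site and the matching baseline score. There is no visit term. The imputation in SAP 8.1.3 covers the diary scores and the in-clinic continuous key secondary outcomes, and the CSFQ-14 is neither.

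**Purpose.** SAP 3.2.2 lists the CSFQ-14 with the exploratory efficacy endpoints, but SAP 10.3 says: "This outcome is considered to be supportive of the product's safety". It appears in neither safety list (SAP 3.2.3 and the opening of SAP 11).

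**Vital signs and laboratory data.** SAP 11.2 and 11.4 both carry this sentence: "ET data will be analyzed with the closest visit that does not have a valid assessment value".

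**The concern.** An ET visit before the last midpoint places the CSFQ-14 score at a visit where no other patient has one and where no CSFQ-14 analysis is planned. The score has been collected, but the Week 14 ANCOVA cannot use it and no imputation replaces it.

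This matters because of what the scale is for. SAP 8.2.6 presents it as a way to assess drug effects on sexual function. Patients who stop early, some of them for intolerance, are among the most informative for that question. If their scores are left out, the comparison describes mainly patients who tolerated treatment to the end or nearly so.

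**Working it through.** **1. Inputs.** Target days come from Protocol 11.3, 11.4 and 11.5.1: Week 2 is Day 15 ("Visit 3 should occur after 2 weeks of treatment, on Day 15 -4/+7 days"), Week 6 is Day 43, Week 10 is Day 71 and Week 14 is Day 99. Planned size is 235 per arm (SAP 6). The readable text gives no dropout rate or timing, so the rates and timings below are assumptions.

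**2. Midpoints.** (15 + 43)/2 = 29; (43 + 71)/2 = 57; (71 + 99)/2 = 85.

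**3. Check against the SAP's own example.** SAP 8.1.2 says: "A subject without valid Week 10 data who early terminates on Day 79 would have the Day 79 data analyzed with the Week 10 data". Day 79 lies between 57 and 85, so it maps to Week 10, as stated. In the companion example a valid Day 72 record is |72 − 71| = 1 day from target and the ET record is |79 − 71| = 8 days away, so Day 72 is kept, again as stated. The rule is reproduced.

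**4. Share of possible ET days that miss Week 14.** For ET on Days 2 to 98 (97 days), with ties going to the earlier visit:

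| Assigned visit | ET days | Number of days |
|---|---|---|
| Week 2 | 2–29 | 28 |
| Week 6 | 30–57 | 28 |
| Week 10 | 58–85 | 28 |
| Week 14 | 86–98 | 13 |

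So 84/97 = 86.6% of possible ET days map to an earlier visit (83/97 = 85.6% if Day 85 goes to Week 14).

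**5. Sensitivity to assumed timing.** Take 98 treatment days, 84 of them before the cut, and let d be the proportion terminating early.
- Evenly spread: 84/98 = 85.7%.
- Constant hazard, λ = −ln(1 − d)/98, share = (1 − e^(−84λ))/d: 86.4% at d = 10%, 87.0% at 20%, 87.8% at 30%.
- Linearly early-loaded: 1 − (14/98)² = 98.0%.
- Linearly late-loaded: (84/98)² = 73.5%.

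The word most fails only if more than half of all ET visits fall in about the last two weeks.

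**6. Scores left out per arm** (assuming every early terminator attends an ET visit and completes the scale; both sexes together):

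| Assumed early termination | ETs per arm | Evenly spread (×84/98) | Late-loaded (×0.735) | Early-loaded (×0.980) |
|---|---|---|---|---|
| 10% | 23.5 | 20.1 | 17.3 | 23.0 |
| 20% | 47.0 | 40.3 | 34.5 | 46.0 |
| 30% | 70.5 | 60.4 | 51.8 | 69.1 |

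**7. Vital signs, same example.** These are scheduled at every visit. With a valid Day 72 record and an ET on Day 79, SAP 8.1.2 excludes the ET record from the by-visit table. SAP 11.4 sends it to the nearest visit without a value. That is Week 14, since |79 − 99| = 20 days, against |79 − 43| = 36 days for Week 6 even if Week 6 were also empty. One record thus gets two different treatments.

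**The case against.** **The ANCOVA may already be meant to take the ET value.** SAP 10.3 names Week 14/ET as the collection time just before the model, and a model without a visit term suits a single post-baseline score. The worked examples in SAP 8.1.2 concern Week 10 data, so they do not show the rule applied to a two-visit scale. This is a fair reading of intent. But the sentence describes collection, the listed endpoint is Week 14, and the windowing rule has no exception.

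**The last-observation rule may cover it.** SAP 10.3 contrasts the CSFQ-14 with the other exploratory analyses, which it says support efficacy. That makes its classification ambiguous. Even if it counts as safety data, the rule in SAP 8.1.2 promises a summary and does not change what enters the ANCOVA.

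**Consequences are limited.** Sexual side effects reported as adverse events, including those leading to discontinuation, are still summarised for the whole Safety population (SAP 11.1 and 11.1.1). The CSFQ-14 lies outside the testing hierarchy, and SAP 8.1.1.2 treats its p-values as descriptive. A Week 14 analysis is also a legitimate choice in itself. All of this stands.

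**Stronger readings that the documents do not support.**
- A reader might infer a completers-only analysis. ET visits after about Day 85 map to Week 14 and remain in it.
- A reader might infer a bias toward showing no harm. That needs dropout to differ between arms in a way related to sexual function, and the readable text gives no figure for it.
- A reader might infer that laboratory values are lost or assigned inconsistently, because laboratory tests share the two-visit schedule. With no scheduled laboratory tests at Weeks 2, 6 or 10, the rules in SAP 8.1.2 and 11.2 give the same visit, and SAP 11.2 already reports the last available assessment. Rows made up only of dropouts are a matter of table layout.

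**Conclusion.** The point holds on the literal text. CSFQ-14 scores from ET visits before about Day 85 have no place in the only specified analysis of that scale. The share of ET scores affected is about 86% if ETs are evenly spread, and 73.5% to 98% across the timings tried. The count of about 20 to 60 per arm rests on assumed early termination of 10 to 30%, even spacing and full ET attendance. SAP 8.2.1 allows for withdrawals without a final visit, so fewer scores may exist to be lost.

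The gap should be closed because the SAP relies on this outcome for safety support and the data are already collected. It does not bear on the primary or key secondary results. The sponsor may intend the Week 14/ET value, but the SAP does not say so. The vital-signs conflict is a separate and smaller matter: SAP 11.4 also reports the last available assessment, so only the by-visit tables differ.

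**What to change.** In SAP 10.3, state that the CSFQ-14 ANCOVA uses each patient's single post-baseline score, from Week 14 or ET, whatever the study day, and that this scale is exempt from the windowing in SAP 8.1.2. Keep the Week 14-only analysis as supportive.

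Separately, reconcile SAP 8.1.2 with SAP 11.4, so that one rule decides where an ET vital-signs record goes when the closest visit already has a value.

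Both are changes of SAP wording and need no new data. The small downside is that the main CSFQ-14 estimate will mix durations of exposure, including terminations during the first two weeks on one tablet. The Week 14-only analysis shows how much that matters.

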8.1.3 Imputation of Missing Data

For individual daily pain scores, since a mean is used in the calculation of the primary endpoint, it is not necessary to replace values missing on random intermittent days; weeks will have average values as long as a single value for that week is present.

Missing weekly pain scores for participants in the ITT population will be imputed via multiple imputation (MI). When the study medication was discontinued due to lack of efficacy (LOE) or due to an AE, missing values will be imputed drawing from the baseline values, conditioned on the non-missing weekly average post-baseline values, of all participants in the ITT population under the assumption that they are missing not at random (MNAR), with a covariate for site. If the study medication was discontinued for any other reason (including impacts from the COVID-19 pandemic), values will be imputed within treatment group using MI under the assumption that they are missing at random (MAR) with covariates for site and the average pain severity score recorded at each time point. The MAR approach will also be applied for sporadic missing values (prior to discontinuation). The MI process will use twenty repeats in the analysis datasets generated; seeds are given in [Appendix D](#). For the purposes of the MI, all sites with less than 10 subjects will be pooled into a single large site; this will be done for both the interim and post interim samples.

The steps will be as follows:

1. Intermittent missing weekly average scores will first be imputed using the Markov Chain Monte Carlo (MCMC) method implemented with the SAS MI procedure, which is appropriate for non-monotonic missing data.
2. For subjects that do not discontinue for LOE or AEs, a MAR imputation will be applied: the monotone missing values will then be multiply imputed with the SAS MI procedure using the monotone regression method. Baseline average and the weekly scores will be included as covariates as well as site; imputation will be done within treatment group.
3. For subjects that discontinue for LOE or AEs, an iterative process will be applied moving through each week. The complete MAR dataset from step 2 above will be used and augmented with subjects missing for the week being imputed at that stage. The non-missing values for the week in question will temporarily be set to the subjects corresponding baseline value, so the data from LOE and AE subjects are imputed for that week drawing from the baseline distribution. This will proceed from Week 1 to Week 14 with the imputed complete dataset for a week serving as the basis for the subsequent week. Covariates at each stage will include the values for the prior weeks (observed, MAR imputed in steps 1& 2, or imputed previously in this step) and site.

The above process will be done independently for the subjects included in the interim analysis and those not in the interim.

Daily sleep diary data will be handled in an identical manner to the pain scores.

Continuous outcomes included in the list of key secondary outcomes that are collected in-clinic will be handled as above, minus the step of creating weekly averages of daily values and with steps being done by visit instead of week.

Subjects with missing PGIC at a given visit will be considered non-responders at that visit for the purposes of treatment comparisons and efficacy claims; additional tabulations will summarize the number and percentage in each category out of non-missing values as well as a count of the missing values.

No missing safety data will be imputed.

8.2 Efficacy Assessments

8.2.1 Average Daily Pain Score

The average daily pain score will be obtained using the daily, 24-hour recall, NRS pain data collected with the diary system. Since a mean is used in the calculation of the primary endpoint, it is not necessary to replace values missing on random intermittent days.

The baseline pain score will be defined as the average of the pain scores from the 7 days prior to the baseline visit. Pain scores must be recorded on at least 5 out of the 7 days immediately preceding the baseline visit in order for the subject to qualify for randomization.

The mean of the daily, subject self-reported, 24-hour recall, pain severity scores for the 7 days of each week will serve as the pain score for that study week. All available values will be used; if a subject has at least one value for the week, the week is non-missing. Because there is a -4 day and +7 day window around the scheduling of Visit 6 (Day 99), the study weeks will be anchored by the timing and completeness of their final study visit. Ideally, subjects appearing in-clinic on Day 99 (defining randomization as Day 1), would have last filled out their diary on Day 98; therefore, "Week 14" would include Days 92-98; the protocol-defined window allows visit 6 as early as Day 95, resulting in a nominal "Week 14" including Days 88-94. Likewise, subjects may appear in-clinic per protocol as late as Day 106, resulting in a "Week 14" interval running from Day 99-105.

Due to impacts from the COVID-19 pandemic, the criteria for calculating the Week 14 average will be marginally relaxed beyond the protocol-specified visit windows to allow for additional flexibility by permitting data collected during Week 13 to be used to calculate the Week 14 average: working backwards from Day 98, the first non-missing day (as early as Day 91) will serve as the LAST day of Week 14 for the purpose of anchoring and any non-missing values in the 6 days prior to that day will contribute to the average. If a subject does not have a non-missing value on/after Day 91, any available data from Day 85-91 will be averaged as Week 14 and Day 91 will serve as the anchor. Subjects without data on/after Day 85 will be missing for Week 14 and handled as described below. Specific examples of calculating the Week 14 pain score are described in [Appendix C](#).

Each week prior to Week 14 will be based on 7-day intervals; depending on the interval selected for "Week 14", this will result in Week 1 having less than 7 days or some "extra" days prior to Week 1. Extra days will be dropped and not included in the analysis; in the case of less than 7 days, the available days will be averaged, as long as there are non-missing values. The earliest

day included in the Week 1 average will be the data entered the day after randomization (covering roughly the 24 hours following their first dose of study drug).

For subjects who withdraw from the study early, that do not have a final study visit or complete the study but do not have data in the 7 days preceding their last visit, the last day of diary data (at or prior to Day 106) will serve as the anchor point for dividing the available data into weeks. First, the nearest nominal end day for a weekly period is identified and this week will be the assigned the data from the 7 days immediately preceding the anchor date. For example, if a subject early terminates on study Day 24, the Week 3 (nominally ending on day 21) average will be based on the 7 days prior to Day 24 (Days 17-23). Lost to follow-up subjects that continue to fill out the diary into Week 14 and beyond will have non-missing values for the Week 14 timepoint for diary outcomes. Day 106 will be the last allowable day to be included in the average.

| Week | Nominal Study Day Intervals |
|----------------------|-----------------------------|
| Baseline | Day -7 to -1 |
| Day of Randomization | Day 1 |
| Week 1 | Day 2 to 7 |
| Week 2 | Day 8 to 14 |
| Week 3 | Day 15 to 21 |
| Week 4 | Day 22 to 28 |
| Week 5 | Day 29 to 35 |
| Week 6 | Day 36 to 42 |
| Week 7 | Day 43 to 49 |
| Week 8 | Day 50 to 56 |
| Week 9 | Day 57 to 63 |
| Week 10 | Day 64 to 70 |
| Week 11 | Day 71 to 77 |
| Week 12 | Day 78 to 84 |
| Week 13 | Day 85 to 91 |
| Week 14 | Day 92 to 98 |

Change from baseline will be defined as the pain score at each week minus the baseline pain score (with baseline and weekly pain scores derived as described above). Thus, negative changes will denote lesser pain and larger negative values will denote greater improvement.

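### SAP 8.2.1 gives two answers on whether the primary Week 14 diary score is observed or imputed when a withdrawal or diary gap leaves the last entry on Days 85–94

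*SAP*

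**What the plan says.** SAP 8.2.1 builds the weekly pain scores in three steps.

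- **Visit anchoring.** In general, "the study weeks will be anchored by the timing and completeness of their final study visit". A Day 99 visit gives Days 92–98, a Day 95 visit Days 88–94, and a Day 106 visit Days 99–105.
- **Back-search (the COVID-19 paragraph).** To find the end of Week 14, "working backwards from Day 98, the first non-missing day (as early as Day 91) will serve as the LAST day of Week 14", and that day and the 6 before it are averaged. "If a subject does not have a non-missing value on/after Day 91, any available data from Day 85-91 will be averaged as Week 14". Then: "Subjects without data on/after Day 85 will be missing for Week 14 and handled as described below". Appendix C tabulates the same rule, with rows for visits on Days 92–94 and before Day 92.
- **Nearest-week rule (the early-withdrawal paragraph).** Its scope opens "For subjects who withdraw from the study early, that do not have a final study visit or complete the study" and, for completers, is limited to those with no diary data in the 7 days before the last visit. For these patients "the last day of diary data (at or prior to Day 106) will serve as the anchor point". The week whose nominal end lies closest is picked, and then "this week will be the assigned the data from the 7 days immediately preceding the anchor date". The worked example is termination on Day 24, which gives Week 3 from Days 17–23. The same paragraph says that patients lost to follow-up whose diary runs into Week 14 have an observed Week 14. It makes Day 106 the last usable day.

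SAP 8.1.3 imputes missing weekly scores. After a stop for an adverse event or lack of efficacy, the draw is from baseline values conditioned on the patient's observed weeks. For other reasons it is a missing-at-random draw within arm. SAP 8.2.2 applies the same windows to the key secondary sleep diary endpoint.

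**The concern.** The back-search has no exception for withdrawals or missed visits. The nearest-week rule is written for exactly those patients and has no exception for entries on or after Day 85. Where both apply they can disagree on whether the primary endpoint exists. With a last entry on Day 91, for example, Days 85–91 are Week 14 under the back-search, while the nearest-week rule gives the last block to Week 13.

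For a patient who stops for an adverse event or lack of efficacy, the choice is between the patient's own late scores and values drawn from the baseline distribution. That touches the estimand in SAP 10.1.1, which assumes that such patients return on average to baseline pain. Completer status for the primary analysis (SAP 8.1.2) also depends on the diary rule in 8.2.1. Divergent programming is a practical risk, because SAP 5.1 and 10.1.2 give the interim analysis to an independent group and the final analyses to the primary vendor.

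**Working it through.** **Inputs.** Nominal end days are 7 × week: 84, 91 and 98 for Weeks 12, 13 and 14 (table in SAP 8.2.1). Let L be the last diary day, with the diary otherwise complete.

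**Reproducing the plan's own figures.** For Day 24, |24 − 21| = 3 and |24 − 28| = 4, so the week is Week 3. The 7 days before Day 24 are 17–23, as printed. The example therefore anchors on the termination day, whereas the text anchors on the last diary day. If Day 23 were the anchor, the 7 days before it would be 16–22 and the last entry would be lost.

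The back-search gives Days L − 6 to L for L ≥ 91. It reproduces the Appendix C rows checked for last entries on Days 98, 94, 93 and 91. It does not reproduce the row for last entry Day 92 (visit Day 93): the rule gives 86–92, but the table prints 85–92, which is eight days.

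**Comparing the rules.** The nearest-week rule picks the week w that minimises |7w − anchor|.

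| Last entry L | Back-search: Week 14 days | Nearest week, anchor L | Nearest week, anchor L + 1 |
|---|---|---|---|
| 84 | missing | 12 | 12 |
| 85–86 | 85 to L | 12 | 12 |
| 87 | 85–87 | 12 | 13 |
| 88–90 | 85 to L | 13 | 13 |
| 91 | 85–91 | 13 | 13 |
| 92 | 86–92 | 13 | 13 |
| 93 | 87–93 | 13 | 13 |
| 94 | 88–94 | 13 | 14 |
| 95 | 89–95 | 14 | 14 |

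The boundaries with anchor L:

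- Day 87 is 3 from 84 and 4 from 91; Day 88 is 4 and 3.
- Day 94 is 3 from 91 and 4 from 98; Day 95 is 4 and 3.

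The rules therefore disagree on ten last-entry days (85–94). If the anchor is the termination day, taken as the day after the last entry, they disagree on nine (85–93). For patients lost to follow-up, the sentence on diaries running into Week 14 (nominally from Day 92) makes Week 14 observed, so seven days remain (85–91).

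**Size, early withdrawals only.** The documents give no figure, so these inputs are assumptions: dropout 20% (range 10–30%), spread evenly over 98 days; every affected patient stops for an adverse event or lack of efficacy; imputed values average 1.5 points (1–2) above the patient's own scores.

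- Share of an arm: 0.20 × 10/98 = 0.0204. Patients: 0.0204 × 235 = 4.8. Shift in the arm mean: 0.0204 × 1.5 = 0.031 points.
- Low end: 0.10 × 10/98 = 0.0102, or 2.4 patients; × 1 = 0.010 points.
- High end: 0.30 × 10/98 = 0.0306, or 7.2 patients; × 2 = 0.061 points.
- Nine days: 0.20 × 9/98 = 0.0184, or 4.3 patients; × 1.5 = 0.028 points.
- Seven days: 0.20 × 7/98 = 0.0143, or 3.4 patients; × 1.5 = 0.021 points.

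The shift is smaller if some stop for other reasons, or to the extent that conditioning on observed weeks pulls the imputed values towards the patient's own.

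**The case against.** The best defence is that the order is signalled. The COVID-19 paragraph passes only patients without data from Day 85 on to the text below it. Its relaxation is not limited by visit status or reason for stopping. Appendix C rules directly on visits before Day 95. Two of the three places agree, and reading the nearest-week rule as residual is natural. This stands as the probable intention. It does not settle the text: the nearest-week paragraph states a wider scope, reaches to Day 106 and discusses diaries that run past Week 14. None of that would be needed if it began only where data end before Day 85.

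Stronger readings are tempting, and the documents do not support them.

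- A reader might infer that the later paragraph leaves Week 14 missing for everyone with a last entry on Days 85–94. It covers only its three groups. A completer with a Day 99 visit and last entry on Day 94 is outside it, and its own sentence on patients lost to follow-up rescues Days 92–94 for them. Nor does it use the word missing for these days; that follows from the week assignment.
- A Week 1 left without diary days by an early anchor might look unhandled. A week with no entries is missing, and SAP 8.1.3 imputes missing weeks.
- It might seem open whether adverse-event or lack-of-efficacy withdrawals may use the back-search. That paragraph makes no exception by reason, and 8.1.3 imputes only what is missing.
- A Day 99 visit with last entry on Day 95 might seem undefined. The back-search gives Days 89–95.
- Visits on Days 100–106 with a complete diary are settled by Appendix C.

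**Conclusion.** Wrong as written, with a small effect. For early withdrawals, patients with no final visit, and completers with no diary data in the 7 days before the last visit, two stated rules in SAP 8.2.1 conflict on whether Week 14 is observed. This is more than missing detail, and Appendix C adds an eight-day week. The extent of the conflict depends on the anchor and on loss to follow-up, as shown above.

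The documents do not say how many patients are affected, and nothing in them sizes the second and third groups. For early withdrawals, the assumed inputs give about 5 of 235 per arm (2–7) and a shift in an arm mean of at most about 0.03 points (0.01–0.06). A reader might infer that one rule favours active treatment. That would depend on how many late withdrawals each arm has, and for what reasons, which the documents do not give. Shifts in the same direction in both arms would partly cancel in the treatment difference. No directional bias or loss of power is claimed. The reason to act is that this is the derivation of the primary variable and the correction is cheap.

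**What to change.** Before unblinding:

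1. In SAP 8.2.1, state that the back-search paragraph and Appendix C decide Week 14 for every patient with an entry on or after Day 85, whatever the visit status or reason for withdrawal. The nearest-week rule then applies only to patients with no entry on or after Day 85. For last entries on Days 99–106 without a usable final visit, anchor on the last entry. Leave the back-search for completers unchanged. Replacing it with a fixed 7 days before Visit 6 would alter the endpoint: for a Day 99 visit with last entry on Day 92, Week 14 would rest on Day 92 alone instead of Days 86–92.
2. In the early-withdrawal paragraph, state one anchor consistent with the Day 24 example, so that the last diary entry is included.
3. In Appendix C, change the Day 93 row to 86–92 and correct the window of plus or minus 4 days to −4/+7, as in Protocol 11.5.1. Use one last allowable day, 105 or 106, both there and in 8.2.1. At present the late row stops at Day 105, while its comment discards only scores after Day 106.

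The cost is SAP wording and one table: no added data, visits or patients.
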